# 21.1.5 Approval/Notification

It will be necessary to obtain IRB/EC approval prior to implementation of any change in the protocol that may affect the scientific soundness or the rights, safety, or welfare of the subjects involved. Notification shall be submitted to the IRB/EC of the study site by the Investigator.

# 21.2 INSTRUCTIONS FOR USE

Refer to the Instruction for Use supplied with this protocol

# 21.3 EQUIPMENT AND SPECIAL INSTRUCTIONS

Not Applicable

# 21.4 Additional Information

Not applicable

# 21.5 **PRINCIPAL INVESTIGATOR OBLIGATIONS (ISO14155:2011)**

- 1. General:
  - a. The role of the PI is to implement and manage the day-to-day conduct of the clinical investigation as well as ensure data integrity and the rights, safety, and well-being of the subjects involved in the clinical investigation.
- 2. Qualification of the PI. The PI shall:
  - a. be qualified by education, training, and experience to assume responsibility for the proper conduct of the clinical investigation in accordance with this International Standard; evidence of such qualifications of the PI and key members of the investigation site team shall be provided to the Sponsor through up-to-date Curriculum Vitae (CV) or other relevant documentation,
  - b. be experienced in the field of application and trained in the use of the investigational device under consideration,
  - c. disclose potential conflicts of interest, including financial, that interfere with the conduct of the clinical investigation or interpretation of results, and
  - d. be knowledgeable with the method of obtaining informed consent.

This document contains information that is confidential and proprietary to Smith + Nephew PLC and Smith + Nephew, Inc. and is intended for use only by Smith + Nephew and its manufacturer. It shall not be reproduced or copied in whole or in part, nor shall the contents be disclosed by any means without prior written permission from Smith + Nephew, nor shall anyone make any use of it that is contrary to the expressed or implied wishes of Smith + Nephew.

Study Protocol	> ∕ smith&nephew
A prospective, multi-center, single arm PMCF study to evaluate the safety and performance of ENTACT ™ (Next Generation) resorbable septal staple system for septoplasty	Number: ENTACT.ENT.PRO.SEP.2019.05
	Version: 2.0, 27Aug2020
······································	Page: Page 87 of 94

- 3. Qualification of investigation site. The PI shall be able to demonstrate that the proposed investigation site:
  - a. has the required number of eligible subjects needed within the agreed recruitment period, and
  - b. has one or more qualified investigators, a qualified investigation site team and adequate facilities for the foreseen duration of the clinical investigation.
- 4. Communication with the IEC. The PI shall:
  - a. provide the Sponsor with copies of any clinical-investigation-related communications between the PI and the IEC,
  - b. comply with the requirements described in 4.5 of ISO 14155:2011.
    - i. Submit to the IEC the following information, any amendments and any additional documentation required by the IEC: the Protocol; IB or equivalent; informed consent form and any other written information provided to subjects; procedures for recruiting subjects and advertising materials, if any; a copy of the CV of the PI(s) for with the IEC has oversight.
    - Provide documentation of the IECs approval/favorable opinion, identifying the documents and amendments on which the opinion was based, to the Sponsor, prior to commencing the clinical investigation.
    - iii. Submit the following to the IEC if required by national regulations, the protocol or IEC, whichever is more stringent:
      - 1. SAEs
      - Requests for deviations, and reports of deviations, if the deviation affects subject's rights, safety, and well-being, or the scientific integrity of the clinical investigation. Document and report to the Sponsor and IEC a report of deviations made to protect the rights, safety, and well-being of human subjects under emergency circumstances.
      - 3. Progress reports, including safety summary and deviations
      - 4. Amendments to any documents already approved by the IEC. CONFIDENTIAL AND PROPRIETARY

This document contains information that is confidential and proprietary to Smith + Nephew PLC and Smith + Nephew, Inc. and is intended for use only by Smith + Nephew and its manufacturer. It shall not be reproduced or copied in whole or in part, nor shall the contents be disclosed by any means without prior written permission from Smith + Nephew, nor shall anyone make any use of it that is contrary to the expressed or implied wishes of Smith + Nephew.

Study Protocol	% smith&nephew
A prospective, multi-center, single arm PMCF study to evaluate the safety and performance of ENTACT ™ (Next Generation) resorbable septal staple system for septoplasty	Number: ENTACT.ENT.PRO.SEP.2019.05
	Version: 2.0, 27Aug2020
······································	Page: Page 88 of 94

- 5. If applicable, notifications of suspension or premature termination
- 6. If applicable, justification and request for resuming the clinical investigation after suspension.
- 7. Clinical investigation report or summary.
- iv. As a minimum, during the clinical investigation, the following information shall be obtained in writing from the IEC prior to implementation:
  - 1. Approval/favorable opinion of amendments
  - 2. Approval of the request for deviations that can affect the subject's rights, safety, and well-being or scientific integrity of the clinical investigation
  - 3. Approval for resumption of a suspended clinical investigation if applicable.
- c. obtain the written and dated approval/favorable opinion of the IEC for the clinical investigation before recruiting subjects and implementing all subsequent amendments, if required,
- d. promptly report any deviations from the protocol that affect the rights, safety or wellbeing of the subject or the scientific integrity of the clinical investigation, including those which occur under emergency circumstances, if required by the IEC, protocol or national regulations. In particular circumstances, the communication with the IEC can be performed by the Sponsor, partly or in full, in which case the Sponsor shall keep the Principal Investigator informed.
- 5. Informed consent process. The PI shall:
  - a. General:
    - Informed consent shall be obtained in writing from the subject and the process shall be documented before any procedure specific to the clinical investigation is applied to the subject; except when special circumstances for emergency treatments apply (see below)
  - b. Process of obtaining informed consent. The general process for obtaining informed consent shall be documented in the protocol and shall comply with the following. These

This document contains information that is confidential and proprietary to Smith + Nephew PLC and Smith + Nephew, Inc. and is intended for use only by Smith + Nephew and its manufacturer. It shall not be reproduced or copied in whole or in part, nor shall the contents be disclosed by any means without prior written permission from Smith + Nephew, nor shall anyone make any use of it that is contrary to the expressed or implied wishes of Smith + Nephew.

Study Protocol	St smith&nephew
A prospective, multi-center, single arm PMCF study to evaluate the safety and performance of ENTACT ™ (Next Generation) resorbable septal staple system for septoplasty	Number: ENTACT.ENT.PRO.SEP.2019.05
	Version: 2.0, 27Aug2020
	Page: Page 89 of 94

requirements also apply with respect to informed consent obtained from a subject's legally authorized representative:

- i. Ensure that the PI or his/her authorized designee conducts the informed consent process
- ii. Include all aspects of the clinical investigation that are relevant to the subject's decision to participate throughout the clinical investigation
- iii. Avoid any coercion or undue improper influence on, or inducement of, the subject to participate
- iv. Not waive or appear to waive the subject's legal rights
- v. Use native non-technical language that is understandable to the subject
- vi. Provide ample time for the subject to read and understand the informed consent form and to consider participation in the clinical investigation
- vii. Include personally dated signatures and the PI or an authorized designee responsible for conducting the informed consent process
- viii. Show how informed consent will be obtained in special circumstances (see below) where the subject is unable to provide him or herself, and
- ix. Ensure important new information is provided to new and existing subjects throughout the clinical investigation.
- c. Special circumstances for informed consent (the following provisions are subject to national regulations):
  - i. Subject needing legally authorized representatives: informed consent may be given by the legally authorized representative only if a subject is unable to make the decision to participate in a clinical investigation (e.g., infant, child, or juvenile, seriously ill or unconscious subject, mentally ill person, mentally handicapped person). In such cases, the subject shall also be informed about the clinical investigation within his/her ability to understand.
  - ii. Subject unable to read or write: informed consent shall be obtained through a supervised oral process if a subject or legally authorized representative is unable

This document contains information that is confidential and proprietary to Smith + Nephew PLC and Smith + Nephew, Inc. and is intended for use only by Smith + Nephew and its manufacturer. It shall not be reproduced or copied in whole or in part, nor shall the contents be disclosed by any means without prior written permission from Smith + Nephew, nor shall anyone make any use of it that is contrary to the expressed or implied wishes of Smith + Nephew.

Study Protocol	> ∕ smith&nephew
A prospective, multi-center, single arm PMCF study to evaluate	Number:
the safety and performance of ENTACT™ (Next Generation)	ENTACT.ENT.PRO.SEP.2019.05
resorbable septal staple system for septoplasty	Version: 2.0, 27Aug2020
	Page: Page 90 of 94

to read or write. An independent witness shall be present throughout the process. The written informed consent form and any other information shall be read aloud and explained to the prospective subject or his/her legally authorized representative and, whenever possible, either shall sign and personally date the informed consent form. The witness also signs and personally dates the informed consent for attesting that the information was accurately explained and that the informed consent was freely given.

- iii. Emergency treatments:
  - For clinical investigations involving emergency treatments, when prior informed consent of the subject is not possible because of the subject's medical condition, the informed consent of the subject's legally authorized representative, if present, shall be requested.
  - 2. When it is not possible to obtain prior informed consent from the subject, and the subject's legally authorized representative, is not available, the subject may still be enrolled if a specific process has been described in the protocol.
  - 3. Arrangements shall be made to inform the subject or legally authorized representative, as soon as possible, about the subject's inclusion in the clinical investigation and about all aspects of the clinical investigation.
  - 4. The subject shall be asked to provide informed consent for continued participation as soon as his/her medical condition allows.
- d. The Principal Investigator may not enroll a subject without obtaining informed consent of the subject or his/her legally authorized representative only when the following conditions are fulfilled: the prospective subject fulfils the emergency conditions and is obviously in a life-threatening situation; no sufficient clinical benefits are anticipated from the currently available treatment; there is a fair possibility that the life-threatening risk to the prospective subject can be avoided if the investigational device is used; anticipated risks are outweighed by the potential benefits of applying the investigational device ; the legally authorized representative cannot be promptly reached and informed.

This document contains information that is confidential and proprietary to Smith + Nephew PLC and Smith + Nephew, Inc. and is intended for use only by Smith + Nephew and its manufacturer. It shall not be reproduced or copied in whole or in part, nor shall the contents be disclosed by any means without prior written permission from Smith + Nephew, nor shall anyone make any use of it that is contrary to the expressed or implied wishes of Smith + Nephew.

Study Protocol	St smith&nephew
A prospective, multi-center, single arm PMCF study to evaluate the safety and performance of ENTACT™ (Next Generation) resorbable septal staple system for septoplasty	Number: ENTACT.ENT.PRO.SEP.2019.05
	Version: 2.0, 27Aug2020
	Page: Page 91 of 94

- e. Information provided to the subject. All information pertinent to the clinical investigation, including at least the following, shall be provided in writing and in native, non-technical language that is understandable to the subject (or the subject's legally authorized representative):
  - i. Description and purpose
  - ii. Potential benefits
  - iii. Risks and inconveniences or the subject and, when applicable, for any embryo, fetus or nursing infant
  - iv. Alternative procedures
  - v. Confidentiality
  - vi. Compensation
  - vii. Anticipated expenses, if any, to be borne by the subject for participating in the clinical investigation
  - viii. Information on the role of Sponsor's representative in the clinical investigation
  - ix. Contact persons
  - x. Statement declaring that new findings or the reasons for any amendment to the protocol that affect the subject's continued participation shall be made available to the subject.
  - xi. Statement indicating that, upon the subject's approval, the subject's personal physician will be informed of the subject's participation in the clinical investigation
  - xii. Termination procedures
- f. Informed consent signature shall contain the following:
  - i. The voluntary agreement to participate in the clinical investigation and follow the investigator's instructions
  - ii. A statement declaring that refusal of participation incurs no penalty for the subject
  - iii. A statement declaring that discontinuation at any time incurs no penalty for the subject
  - iv. A statement with regard to the possible consequences of withdrawal

This document contains information that is confidential and proprietary to Smith + Nephew PLC and Smith + Nephew, Inc. and is intended for use only by Smith + Nephew and its manufacturer. It shall not be reproduced or copied in whole or in part, nor shall the contents be disclosed by any means without prior written permission from Smith + Nephew, nor shall anyone make any use of it that is contrary to the expressed or implied wishes of Smith + Nephew.

Study Protocol	St smith&nephew
A prospective, multi-center, single arm PMCF study to evaluate the safety and performance of ENTACT™ (Next Generation) resorbable septal staple system for septoplasty	Number: ENTACT.ENT.PRO.SEP.2019.05
	Version: 2.0, 27Aug2020
	Page: Page 92 of 94

- v. An acknowledgment of the information provided and confirmation that all the subject's questions were answered
- vi. A statement confirming that the subject or his/her legally authorized representative agrees to the use of the subject's relevant personal data for the purpose of the clinical investigation
- vii. A statement confirming that the subject or his/her legally authorized representative agrees that Sponsor's representatives, regulatory authorities and IEC representatives will be granted direct access to the subject's medical records.
- g. New information: if new information becomes available that can significantly affect a subject's future health and medical care, that information shall be provided to the subject(s) affected in written form. If relevant, all affected subjects shall be asked to confirm their continuing consent in writing.
- h. Ensure compliance with the applicable regulatory requirements and ethical principles for the process of obtaining informed consent, and
- i. Ensure and document appropriate training if an authorized designee is appointed to conduct the informed consent process.
- 6. Compliance with the protocol. The Principal Investigator shall:
  - a. indicate his/her acceptance of the protocol in writing,
  - b. conduct the clinical investigation in compliance with the protocol,
  - c. create and maintain source documents throughout the clinical investigation and make them available as requested during monitoring visits or audits,
  - d. ensure that the investigational device is used solely by authorized users as specified in6.2, and in accordance with the protocol and instructions for use,
  - e. propose to the Sponsor any appropriate modification(s) of the protocol or investigational device or of the use of the investigational device,
  - f. refrain from implementing any modifications to the protocol without agreement from the Sponsor, IEC and regulatory authorities, if required,

This document contains information that is confidential and proprietary to Smith + Nephew PLC and Smith + Nephew, Inc. and is intended for use only by Smith + Nephew and its manufacturer. It shall not be reproduced or copied in whole or in part, nor shall the contents be disclosed by any means without prior written permission from Smith + Nephew, nor shall anyone make any use of it that is contrary to the expressed or implied wishes of Smith + Nephew.

Study Protocol	Smith&nephew
A prospective, multi-center, single arm PMCF study to evaluate the safety and performance of ENTACT™ (Next Generation) resorbable septal staple system for septoplasty	Number: ENTACT.ENT.PRO.SEP.2019.05
	Version: 2.0, 27Aug2020
	Page: Page 93 of 94

- g. document and explain any deviation from the approved protocol that occurred during the course of the clinical investigation,
- h. ensure that an adequate investigation site team and facilities exist and are maintained and documented during the clinical investigation,
- i. ensure that maintenance and calibration of the equipment relevant for the assessment of the clinical investigation is appropriately performed and documented, where applicable,
- j. ensure the accuracy, completeness, legibility, and timeliness of the data reported to the Sponsor in the CRF and in all required reports,
- k. maintain the device accountability records,
- I. allow and support the Sponsor to perform monitoring and auditing activities,
- m. be accessible to the monitor and respond to questions during monitoring visits,
- n. allow and support regulatory authorities and the IEC when performing auditing activities,
- o. ensure that all clinical-investigation-related records are retained as required taking measures to prevent accidental or premature destruction, and
- p. review and sign the clinical investigation report, as applicable.
- 7. Medical care of subjects. The Principal Investigator shall
  - a. provide adequate medical care to a subject during and after a subject's participation in a clinical investigation in the case of adverse events,
  - b. inform the subject of the nature and possible cause of any adverse events experienced,
  - c. provide the subject with the necessary instructions on proper use, handling, storage, and return of the investigational device, when it is used or operated by the subject,
  - d. inform the subject of any new significant findings occurring during the clinical investigation, including the need for additional medical care that may be required,
  - e. provide the subject with well-defined procedures for possible emergency situations related to the clinical investigation, and make the necessary arrangements for

This document contains information that is confidential and proprietary to Smith + Nephew PLC and Smith + Nephew, Inc. and is intended for use only by Smith + Nephew and its manufacturer. It shall not be reproduced or copied in whole or in part, nor shall the contents be disclosed by any means without prior written permission from Smith + Nephew, nor shall anyone make any use of it that is contrary to the expressed or implied wishes of Smith + Nephew.

Study Protocol	Smith&nephew
A prospective, multi-center, single arm PMCF study to evaluate the safety and performance of ENTACT™ (Next Generation) resorbable septal staple system for septoplasty	Number: ENTACT.ENT.PRO.SEP.2019.05
	Version: 2.0, 27Aug2020
	Page: Page 94 of 94

emergency treatment, including decoding procedures for blinded/masked clinical investigations, as needed,

- f. ensure that clinical records are clearly marked to indicate that the subject is enrolled in a particular clinical investigation,
- g. if appropriate, subjects enrolled in the clinical investigation shall be provided with some means of showing their participation in the clinical investigation, together with identification and compliance information for concomitant treatment measures (contact address and telephone numbers shall be provided),
- h. inform, with the subject's approval or when required by national regulations, the subject's personal physician about the subject's participation in the clinical investigation, and
- i. make all reasonable efforts to ascertain the reason(s) for a subject's premature withdrawal from the clinical investigation while fully respecting the subject's rights.
- 8. Safety reporting. The Principal Investigator shall:
  - a. record every adverse event and observed device deficiency, together with an assessment,
  - report to the Sponsor, without unjustified delay, all serious adverse events and device deficiencies that could have led to a serious adverse device effect; this information shall be promptly followed by detailed written reports, as specified in the protocol,
  - report to the IEC serious adverse events and device deficiencies that could have led to a serious adverse device effect, if required by the national regulations or protocol or by the IEC,
  - report to regulatory authorities serious adverse events and device deficiencies that could have led to a serious adverse device effect, as required by the national regulations, and
  - e. supply the Sponsor, upon Sponsor's request, with any additional information related to the safety reporting of a particular event.

This document contains information that is confidential and proprietary to Smith + Nephew PLC and Smith + Nephew, Inc. and is intended for use only by Smith + Nephew and its manufacturer. It shall not be reproduced or copied in whole or in part, nor shall the contents be disclosed by any means without prior written permission from Smith + Nephew, nor shall anyone make any use of it that is contrary to the expressed or implied wishes of Smith + Nephew.

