## 9. STUDY PROCEDURES

### 9.1 VISITS AND EXAMINATIONS

None of the listed activities are undertaken by Sponsor personnel.

Schedule of Events	Patient screening and		Post-operative patient visits		
	surgery				
	Screening/Pre- Operative ≤ 30 days	Surgery Day 0	FU time point Day 5±2	FU time point Day 21±7	FU time point Day 42±7
Informed Consent	Х	-	-	-	-
Inclusion/Exclusion	Х	-	-	-	-
Demographics: Medical History	Х	-	-	-	-
Operative data (Intra- operative delivery success, intra- operative time to deploy staples to complete septoplasty)	-	х	-	-	-
Discharge data	-	Х	-	-	-
Visual assessment of nasal cavity	-	-	Х	Х	х
NOSE score	Х	-	Х	Х	Х
Visual Analog Scale	Х	-	Х	Х	Х
Concomitant Medications, Procedures	Х	х	х	х	х
Safety assessment (AE/SAE/ADE/DD)	-	Х	Х	Х	X

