### ----- Do not proceed until consent has been obtained -----

- 2. Obtain demographic information and medical history, including information on all concomitant medications/therapies.
- 3. Screen the subject for protocol inclusion/exclusion criteria.
- 4. Assign the subject a Subject ID.
- 5. Complete Screening and Enrollment Log.
- 6. Complete NOSE score assessment and VAS pain score.

This document contains information that is confidential and proprietary to Smith + Nephew PLC and Smith + Nephew, Inc. and is intended for use only by Smith + Nephew and its manufacturer. It shall not be reproduced or copied in whole or in part, nor shall the contents be disclosed by any means without prior written permission from Smith + Nephew, nor shall anyone make any use of it that is contrary to the expressed or implied wishes of Smith + Nephew.

Study Protocol	% smith&nephew
A prospective, multi-center, single arm PMCF study to evaluate	Number:
the safety and performance of ENTACT™ (Next Generation) resorbable septal staple system for septoplasty	ENTACT.ENT.PRO.SEP.2019.05
	Version: 2.0, 27Aug2020
	Page: Page 49 of 94

7. Subjects will be instructed to return for the Operation Visit (Procedure) as scheduled by the site.

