# 9.1.3 Follow-up Visit (Visit 3) Day 5 (± 2 days)

- Query subject regarding any changes in general health and the use of concomitant medications.
- 2. Record assessment of nasal cavity.

This document contains information that is confidential and proprietary to Smith + Nephew PLC and Smith + Nephew, Inc. and is intended for use only by Smith + Nephew and its manufacturer. It shall not be reproduced or copied in whole or in part, nor shall the contents be disclosed by any means without prior written permission from Smith + Nephew, nor shall anyone make any use of it that is contrary to the expressed or implied wishes of Smith + Nephew.

Study Protocol	> √ smith&nephew
A prospective, multi-center, single arm PMCF study to evaluate the safety and performance of ENTACT™ (Next Generation) resorbable septal staple system for septoplasty	Number: ENTACT.ENT.PRO.SEP.2019.05
	Version: 2.0, 27Aug2020
	Page: Page 50 of 94

- If any adverse device effects or device deficiencies are observed or reported, they must be recorded as instructed in Section 12, adverse events and device deficiencies. Also record concomitant medications/therapies used to treat AEs.
- 4. Complete NOSE score assessment and VAS pain score.
- 5. Instruct the subject on follow-up procedures, including returning the treatment facility at 21 days post-operative (± 7) days for follow-up visit.
- 6. If applicable, complete an End of Study CRF.

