## 9.1.4 Follow-up Visit (Visit 4) Day 21 (± 7 days)

- 1. Query subject regarding any changes in general health and the use of concomitant medications.
- 2. Record assessment of nasal cavity.
- If any adverse device effects or device deficiencies are observed or reported, they must be recorded as instructed in Section 12, adverse events and device deficiencies. Also record concomitant medications/therapies used to treat AEs.
- 4. Complete NOSE score assessment and VAS pain score.
- 5. Instruct the subject on follow-up procedures, including returning the treatment facility at 42 days post-operative (± 7) days for follow-up visit.
- 6. If applicable, complete an End of Study CRF.

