## 10.4.2 Analysis of Secondary Endpoints

Nasal cavity assessments at day 5 and day 42 will be summarized and presented as count and percentage of each criterion.

Successful staple deployment at the operative visit will be summarized by count and percentage. A 95% exact confidence interval for a single proportion will be presented for successful staple deployment using the Clopper-Pearson method. The number of staples used and whether the stapler misfired will also be presented.

Total operating room time will be calculated and summarized using descriptive statistics and will be presented descriptively by septoplasty only cases as well as septoplasty and turbinate reduction cases.

Intra-operative time to deploy staples to complete septoplasty, calculated as time between start of closure to when the stapler was handed back to the scrub nurse, will be summarized and presented descriptively by septoplasty only cases as well as septoplasty and turbinate reduction cases.

NOSE score will be calculated and summary statistics will be presented by visit. Change in NOSE score from the pre-operative visit to each post-operative visit will also be presented and an ANOVA model will be used to assess statistical significance.

This document contains information that is confidential and proprietary to Smith + Nephew PLC and Smith + Nephew, Inc. and is intended for use only by Smith + Nephew and its manufacturer. It shall not be reproduced or copied in whole or in part, nor shall the contents be disclosed by any means without prior written permission from Smith + Nephew, nor shall anyone make any use of it that is contrary to the expressed or implied wishes of Smith + Nephew.

Study Protocol	% smith&nephew
A prospective, multi-center, single arm PMCF study to evaluate the safety and performance of ENTACT™ (Next Generation) resorbable septal staple system for septoplasty	Number: ENTACT.ENT.PRO.SEP.2019.05
	Version: 2.0, 27Aug2020
	Page: Page 57 of 94

The VAS Pain score will be summarized by visit. Change in VAS Pain score from the preoperative visit to each post-operative visit will also be presented and an ANOVA model will be used to assess statistical significance.

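### The follow-up visits list the nasal exam before NOSE and VAS pain, and nothing requires the patient-reported scores to be completed first

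*Combined protocol and SAP*

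**What the plan says.** The three follow-up visits (Sections 9.1.3, 9.1.4 and 9.1.5) share one numbered list. Item 1 is a query on health and medication. Item 2 is "Record assessment of nasal cavity". Item 3 reads "If any adverse device effects or device deficiencies are observed or reported, they must be recorded as instructed in Section 12". Item 4 is "Complete NOSE score assessment and VAS pain score".

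Table 9.1.1-1 lists the visual assessment of the nasal cavity, then NOSE, then VAS, then concomitant medications and procedures, and only then "Safety assessment (AE/SAE/ADE/DD").

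At Visit 1 (Section 9.1.1) the two scores are item 6, after consent, demographics and medical history, eligibility screening, Subject ID and the log. The table schedules no visual nasal assessment and no safety assessment at Screening.

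Sections 9.2.1 and 9.2.2 describe the two instruments and the visits at which they are used. Neither says where in the visit they are completed. Section 10.4.2 states that "Change in NOSE score from the pre-operative visit to each post-operative visit will also be presented", with an ANOVA model for significance, and treats VAS pain the same way. Section 10.1 sets the two-sided 5% level. Sections 8.2.1 and 8.2.2 confirm that the study is neither randomized nor blinded.

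Separately, Appendix 21.5, item 7b, obliges the Principal Investigator to "inform the subject of the nature and possible cause of any adverse events experienced", without naming a visit or a time.

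**The concern.** NOSE and VAS pain are self-ratings, and the analysis looks at their change from before surgery. A subject who fills in the pain line after the operated cavity has been examined, or after talking with staff about how the repair looks, may give a different answer from the one given on arrival. VAS is the more exposed of the two. It asks about pain where the staples were placed, Section 9.2.2 gives it no recall period, and the listed step just before it looks at that same area.

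A shift that affects mainly the post-operative ratings passes into the change score, and a single-arm open-label study has no second group in which it would cancel. Section 8.4.3 already protects the clinician's assessment by giving follow-up exams to investigators not involved in the procedure. Nothing comparable protects the patient's own ratings. Because no order is stated, practice may also differ between the (up to three) sites.

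**Working it through.** **1. The listed orders side by side.**

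| Element | 9.1.3 to 9.1.5 (Days 5, 21, 42) | Table 9.1.1-1 | 9.1.1 (Visit 1) |
|---|---|---|---|
| Nasal cavity assessment | item 2, before scores | above scores | none scheduled |
| Adverse effect / safety item | item 3, before scores | below scores | none scheduled |
| NOSE and VAS pain | item 4 | between the two | item 6 |

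The lists and the table agree that the exam comes before the scores. They disagree on the safety item.

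**2. Is the order binding?** The documents do not say so. Where sequence matters the protocol states it, as at Visit 1: "Do not proceed until consent has been obtained". Section 7.6 assigns the Subject ID at consent, although Section 9.1.1 numbers it fourth, after history and screening. The lists therefore show a likely order of work, not a mandated one.

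**3. Is there a baseline difference?** In part. The scheduled visual assessment precedes only the post-operative scores. However, the Visit 1 scores follow history-taking and eligibility screening, and that screening includes judging whether the septal deviation is clinically significant. Baseline is not shown to be free of clinical evaluation of the nose.

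**4. Does the protocol say subjects are told findings before scoring?** No. Item 3 is conditional and concerns recording. The Appendix 21.5 duties to "inform the subject of the nature and possible cause of any adverse events experienced" and to "inform the subject of any new significant findings occurring during the clinical investigation" give no time point and apply only where there is an event or a finding.

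**5. Scale, purely as illustration.** The plan gives no figure to reproduce here: no SD of change for this study and no size of bias. Assume a true change of zero and a common shift of b standard deviations of the change score. Use a two-sided 5% one-sample t-test on change as a stand-in for the ANOVA, whose form is not specified. The noncentrality is b × √n. With n = 36 (Section 11, after drop-out), √n = 6:

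| Assumed shift b | Noncentrality | Rejection probability, n = 36 | Same, n = 40 |
|---|---|---|---|
| 0 | 0 | 5.0% | 5.0% |
| 0.1 | 0.6 | 9.0% | 9.5% |
| 0.2 | 1.2 | 21.5% | 23.5% |
| 0.3 | 1.8 | 41.7% | 45.7% |

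On the VAS, a 3 mm shift with an assumed SD of 15 mm is 3/15 = 0.2 SD. With an assumed SD of 25 mm it is 3/25 = 0.12 SD, and the rejection probability is 10.8%. These rows say what a shift would do if there were one. They are not evidence that there is one.

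**The case against.** The strongest case on the other side is that this is a missing instruction on two secondary endpoints, with a speculative mechanism. The exam is described as a visual assessment, and nothing says that it hurts. NOSE asks about problems since the last visit, which limits what a same-day exam can do to it. The earlier randomized study of the stapler cited in Section 4.2.1 reports a NOSE improvement of 10 on a 20-point scale, so a small shift is unlikely to decide significance there. The primary endpoint is a clinician's composite, and neither marketing claim in Section 5.4 uses these scores. All of this stands, and it is why the point is graded low.

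A reader might infer something stronger: that every post-operative score is given just after the subject has heard about the repair or about adverse events, because Appendix 21.5 obliges the investigator to inform. The documents do not support that. The duties carry no timing, they reach only subjects with an event or significant finding, and Table 9.1.1-1 places the safety assessment after the scores. Only the exam-before-score order applies to every follow-up visit.

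What the objection does not remove is that the listed order is the less protective one, that no text corrects it, and that the lists and the table differ on the safety item.

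**Conclusion.** The point holds as a free improvement of low severity. The protocol lists the nasal exam before NOSE and VAS pain at all three post-operative visits, nowhere requires the scores to come first, and tests change from pre-op without a control group or blinding. If sites follow the listed order, the exam and any discussion of findings can influence the ratings, most plausibly VAS pain.

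This rests on two assumptions: that sites tend to follow the numbered lists, and that a self-rating can be influenced by an exam or conversation just before it. Neither the size nor the direction of an effect can be determined from the documents: discomfort from an exam would raise VAS, while reassurance could lower NOSE. A reader might take the illustrative rejection rates as the study's actual false-positive rates, or take the baseline scores as free of any such influence. Neither reading is supported. The primary endpoint is unaffected.

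**What to change.** In Sections 9.1.3, 9.1.4 and 9.1.5, make self-completion of NOSE and VAS pain step 1, before the health query, the nasal exam and any discussion of findings or adverse events. In Section 9.1.1, place it straight after consent, so that baseline and follow-up scores are collected alike. State in Sections 9.2.1 and 9.2.2 that this order is required. Reorder the rows of Table 9.1.1-1 to match, which also removes its difference from the visit lists on the safety item. The investigator's duties to inform in Appendix 21.5 stay as they are.

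The cost is a reordering of existing steps: no added procedure, visit or staff.
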